The lomitapide US Prescribing Information (PI) and the EU Summary of Product Characteristics (SPC) include a contraindication for use during pregnancy and instructions that females of reproductive potential should have a negative pregnancy test before starting lomitapide and use effective contraception during therapy with lomitapide.

The PER will be conducted in all countries that are included in the Lomitapide Observational Worldwide Evaluation Registry (LOWER), Protocol AEGR-733-025. Information on any spontaneous or literature reports of pregnancies with lomitapide exposure from patients who are not enrolled in the PER will be added to the PER analyses once the pregnancies have been followed to outcome by the Aegerion Safety Department or its designee.

The PER will collect data on any pregnancies that occur in women exposed to lomitapide in the 30 days prior to conception or during pregnancy. Due to the rarity of HoFH and the contraindications for lomitapide use during pregnancy, it is anticipated that the PER will collect few pregnancies; however, all eligible pregnancies, whether retrospective or prospective, will be enroled. The pregnancies that are recorded in and reported from the PER will provide valuable information on birth outcomes following exposure to lomitapide. While the outcomes of primary interest are major congenital anomalies, full descriptions of all pregnancies, birth outcomes, and loss-to-follow-up will be provided in the planned annuals reports; the descriptions will include birth weight, gestational age, whether the delivery was a multiple birth, and age at diagnosis of any paediatric abnormalities.

Confidential Page 19 of 54

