9.7.2 Estimates of Incidence of Birth Defects

For the primary analysis, the incidence of birth defects reported to the PER is calculated by dividing the number of birth defects by the total number of live births. Pregnancy losses with reported birth defects at ≥20 gestation weeks are included in the numerator to increase sensitivity and to allow comparison with the US national population-based birth defect surveillance system (CDC MACDP) that uses this convention.

A secondary analysis, including pregnancy losses with reported birth defects occurring at <20 gestation weeks in the calculation of risk, will be conducted. The analysis of birth defects outcomes will be stratified by earliest trimester of exposure, maternal age, and other maternal risk factors, as appropriate. Statistical analysis will consider maternal age as it influences the rate of chromosomal abnormalities.

Ninety-five percent confidence intervals for birth defect rates will be calculated to assess the degrees of confidence. The prevalence in exposed pregnancies will be compared with the prevalence observed in the population-based birth defect data sources. The strength of evidence for lack of elevated levels of major birth defects in pregnancy exposures to lomitapide will be assessed by comparing the observed proportion of birth defects in the PER with rates from the external birth defect data sources, using a chi-square test.

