9.9.1 Comparison Population

Outcomes data will be compared to published rates such as those from the MACDP.

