ANNEX 2. ENCEPP CHECKLIST FOR STUDY PROTOCOLS

Confidential Page 45 of 54

ENCePP Checklist for Study Protocols (Revision 1)

Section 1: Research question	Yes	No	N/A	Page Number(s)
 1.1 Does the formulation of the research question clearly explain: 1.1.1 Why the study is conducted? (e.g. to address an important public health concern, a risk identified in the risk management plan, an emerging safety issue) 1.1.2 The objectives of the study? 				18-19
 1.2 Does the formulation of the research question specify: 1.2.1 The target population? (i.e. population or subgroup to whom the study results are intended to be generalised) 1.2.2 Which formal hypothesis(-es) is (are) to be tested? 1.2.3 If applicable, that there is no a priori hypothesis? 				20

Comments: This is an observational study with descriptive analyses and no hypothesis testing.

Confidential Page 46 of 54

Section 2: Source and study populations	Yes	No	N/A	Page Number(s)
2.1 Is the source population described?				20
2.2 Is the planned study population defined in terms of:				
2.2.1 Study time period?	\boxtimes			17
2.2.2 Age and sex?				21
2.2.3 Country of origin?	\boxtimes			2
2.2.4 Disease/indication?				18

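### Section 9.7.2 rests the judgement on lack of elevated birth-defect risk on a chi-square test of equality, which cannot support that conclusion and is unreliable at the few pregnancies expected

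*Protocol*

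**What the plan says.** Section 9.7.2 plans an external comparison of the primary outcome, major birth defects: "The prevalence in exposed pregnancies will be compared with the prevalence observed in the population-based birth defect data sources". It gives that comparison a purpose and a method: "The strength of evidence for lack of elevated levels of major birth defects in pregnancy exposures to lomitapide will be assessed", by setting the registry proportion against "rates from the external birth defect data sources, using a chi-square test". It states no largest excess to be ruled out, no alternative for small counts and no rule for reading the result. Section 9.9.1 names the kind of comparator but no figure: "Outcomes data will be compared to published rates such as those from the MACDP".

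Section 9.7.2 also says: "Ninety-five percent confidence intervals for birth defect rates will be calculated to assess the degrees of confidence". Section 9.7 likewise promises 95% confidence intervals for the primary analyses. Neither section links those intervals to the judgement on lack of elevation.

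On size, Section 7 says "it is anticipated that the PER will collect few pregnancies". Section 4.2 says much the same, and Section 9.5 says the number of candidates cannot be estimated accurately. The comment to Section 1 of the checklist in Annex 2 reads: "This is an observational study with descriptive analyses and no hypothesis testing". Section 4.9 also describes the analyses as descriptive.

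**The concern.** A chi-square test against a reference rate looks for a difference. Failing to find one does not support equality, and the fewer the data, the easier it is to fail. Without a stated margin, no result of this test can supply the conclusion that the sentence assigns to it. This fault does not depend on sample size.

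Two further points add to it. At the counts this registry is likely to see, the chi-square distribution approximates the test statistic poorly. And the document both plans a hypothesis test on its primary outcome and says that it plans none.

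At stake is how a small safety registry is read. Section 7 reports teratogenicity in rats and ferrets, and reports are to be issued annually. An uninformative result could be set down as support for no increase.

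**Working it through.** The protocol gives no sample size, power, margin or reference rate, so it has no figure to reproduce.

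**Inputs**
- Test: chi-square against external rates (Section 9.7.2).
- Significance level: not stated; assumed 5% two-sided, in line with the planned 95% intervals.
- Reference rate p0: not stated; assumed 3%, range 2% to 5%.
- Live births n: not stated; assumed 5 to 50.
- Simplifications: the number of defects x is taken as binomial in n live births, and the external rate as known without error.

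**Step 1. One-sample Pearson statistic.** X² = (x − n·p0)² / [n·p0·(1 − p0)], significant if above 3.84.

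For 0 of 10 at 3%: X² = 0.3² / (0.3 × 0.97) = 0.09 / 0.291 = 0.31, so p = 0.58. The Clopper-Pearson 95% upper limit for zero cases is 1 − 0.025^(1/n). For n = 10 this is 1 − 0.025^0.1 = 30.8%, or 30.8 / 3 = 10.3 times the reference. The test sees nothing, while the data are compatible with a tenfold excess.

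**Step 2. Chance of missing a real increase.** At p0 = 3% and n = 10, X² first exceeds 3.84 at x = 2. If the true risk is tripled (9%), the probability of at most one case is 0.91^10 + 10 × 0.09 × 0.91^9 = 0.389 + 0.385 = 0.775 (0.7746 before rounding, so 77%). The other rows are found in the same way.

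| n | significant from x = | missed, risk doubled | missed, risk tripled |
|---|---|---|---|
| 10 | 2 | 88% | 77% |
| 20 | 3 | 89% | 73% |
| 30 | 3 | 73% | 49% |
| 50 | 4 | 65% | 33% |

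For a tripled risk, the miss rate at n = 10 is 88% with a 2% reference and 54% with a 5% reference. At n = 50 it is 42% and 22%.

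**Step 3. Quality of the approximation.** An expected count of 5, the usual rule of thumb, needs n = 5 / p0: 5 / 0.03 = 167 live births (250 at 2%, 100 at 5%).

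- 1 of 5 at 3%: X² = 0.85² / (0.15 × 0.97) = 4.97, p = 0.026. Exact binomial: 1 − 0.97^5 = 0.141.
- 2 of 10 at 3%: X² = 1.7² / 0.291 = 9.93, p = 0.0016. Exact binomial: 0.035.

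The actual size of the nominal 5% test at 3% is 14.1% at n = 5, 3.5% at n = 10, 2.1% at n = 20, 6.0% at n = 30 and 6.3% at n = 50.

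At 3%, the chi-square and the exact binomial test reject from the same count at n = 10 (two cases) and at n = 20 (three). They differ by one case at n = 5, 30 and 50. So at n = 10 and 20 the p-value is wrong but the 5% decision is not. This agreement belongs to the 3% assumption; at 5%, for instance, the two tests differ at n = 10.

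**Step 4. What the interval could support.** With zero defects, the exact upper limit falls below twice a 3% reference when 0.94^n < 0.025, that is n > ln(0.025) / ln(0.94) = 59.6, so 60 live births (91 at 2%, 36 at 5%).

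**The case against.** Four points can be made for the plan.

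**Confidence intervals are already planned.** This stands. A reader might take the chi-square for the only inferential statement on the primary outcome, but Sections 9.7 and 9.7.2 both promise 95% intervals, and an exact interval would put the 30.8% limit next to p = 0.58. What remains is that the judgement on lack of elevation is given to the test and not to the interval.

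**The plan never says that a non-significant result shows safety.** This is correct. A reader might infer that the plan labels non-significance as proof of no increase; the text speaks of assessing strength of evidence and gives no decision rule. A Steering Committee with biostatistical and teratology expertise also assists interpretation (Section 9.4.1). But the sentence gives the test that purpose, so the misreading is an inference that the wording invites.

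**The chi-square is not wrong everywhere.** Also correct. A reader might infer that it manufactures alarms at every small size. The 14% size belongs to n = 5; from 10 to 50 live births it lies between 2% and 6% at the 3% reference. For 2 of 10, the exact test rejects as well.

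**Low power comes from rarity, not from the test.** True, and the protocol is open about the rarity. An exact test would miss a tripled risk more often: 72% against 49% at n = 30, and 53% against 33% at n = 50. Changing the test alone is therefore no remedy.

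That the analysis plan may add detail does not answer the point, because the protocol itself fixes both the test and its purpose.

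**Conclusion.** The concern holds in this form: the judgement on lack of elevated risk is attached to a test that cannot deliver it, with no margin, in a registry expected to be small. The logical fault and the conflict with Annex 2 follow from the text alone and need no assumption.

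The sizes depend on the assumed reference rate, registry size and 5% level. Across references of 2% to 5% and 10 to 50 live births, a tripled risk is missed between 22% and 88% of the time, so the fault is serious for a very small registry and less so for large excesses near 50 live births. The weakness of the approximation is secondary: p-values can be far too small, but whether the 5% decision changes varies with n and with the reference rate.

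**What to change.** - Delete the chi-square sentence in Section 9.7.2. This also brings the section into line with Annex 2.
- Base the judgement on the already planned 95% interval, computed by the Clopper-Pearson method for prospective reports. Name the reference rate and state which multiple of it the upper limit excludes.
- State that an interval which includes such an excess, or any non-significant p-value, is inconclusive and is not evidence of no increase.
- If a p-value is kept, make it exact and label it descriptive. That corrects the p-value but does not by itself cure the logical fault, and Annex 2 would then have to acknowledge it.

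The cost is wording in the protocol, carried through to the analysis plan, with no change to data collection. The price is a less favourable conclusion: at a 3% reference, fewer than 60 live births cannot exclude a doubling even with zero defects.

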9.8 Quality Control

9.8.1 Coordinating Centre Staff Training and Initiation

CC staff will be fully trained on the study requirements and use of the EDC system with retraining should the EDC be modified during the existence of the PER.

9.8.2 Data Quality Assurance

Data quality will be monitored including annual reviews by an Aegerion or designee team member including a senior scientist with prior experience in the evaluation of PER data.

Confidential Page 36 of 54

Necessary modifications will be suggested and, as appropriate, submitted as a request to the appropriate Regulatory Authorities.

9.9 Limitations of the Research Methods

The PER is observational epidemiologic research with limitations inherent in a non-randomized design.

9.9.1 Comparison Population

Outcomes data will be compared to published rates such as those from the MACDP.

9.9.2 Other Aspects

9.9.2.1 Regulatory Authorities

The protocol will be submitted to applicable regulatory authorities in accordance with the regulations of the countries involved in the study.

9.9.2.2 Protocol Modifications

Amendments to the protocol may only be made by Aegerion Pharmaceuticals. All protocol amendments must be approved by the Regulatory Authorities (RA) and Institutional Review Board/Independent Ethics Committees (IRB/IEC) if required, prior to implementation of the amendment

10. PROTECTION OF HUMAN SUBJECTS

10.1 Informed Consent

Written consent will be obtained from all PER participants. When a patient reports her own pregnancy to the PER, in countries where direct patient contact is allowed, the CC will first obtain verbal consent in order that enrolment information can be documented for sending a consent form and RMI form to the patient for signature.

10.2 Data Privacy

In any presentations or in publications of the results of the study, the patients' identities will remain anonymous and confidential. Aegerion Pharmaceuticals, its designee(s), and various

Confidential Page 37 of 54

government health agencies may inspect the records of the study. Every effort will be made to keep the patients' personal medical data confidential.

10.3 Independent Ethics Committee or Institutional Review Board

Prior to the collection of any study related data, IRB/IEC approval of the protocol, informed consent and all patient enrolment materials will be obtained in each country, as applicable.

The study will be conducted in accordance with the ethical principles originating from the Declaration of Helsinki, applicable privacy laws, and local regulations. This non-interventional study will be conducted in accordance with the Guidelines for Good Pharmacoepidemiology Practices (GPP) issued by the International Society for Pharmacoepidemiology. When applicable, an IRB/IEC will review and approve the protocol before any patient is enroled. Appropriate informed consent will be obtained from participating patients.

11. MANAGEMENT AND REPORTING OF ADVERSE EVENTS/ADVERSE REACTIONS

11.1 Definitions

The definitions to follow are in accordance with those outlined in the current protocol and in the Guideline on Good Pharmacovigilance Practices (GVP).

11.2 Adverse Event

Any untoward medical occurrence in a patient or clinical investigation subject administered a pharmaceutical product and which does not necessarily have a causal relationship with this treatment. An AE can, therefore, be any unfavourable and unintended sign (including an abnormal laboratory finding), symptom, or disease temporally associated with the use of a medicinal (investigational) product, whether or not related to the medicinal (investigational) product.

11.3 Serious Adverse Event

A Serious Adverse Event (SAE) is any untoward medical occurrence that at any dose:

Results in death.

Is life-threatening.

Confidential Page 38 of 54

Note: The term "life-threatening" refers to an event which, in the view of the investigator, places the subject at immediate risk of death from the time of the event as it occurred; it does not refer to an event which hypothetically might have caused death had it been more severe.

Required inpatient hospitalisation or prolongation of an existing hospitalisation.

A pre-existing event or condition that results in hospitalization should be recorded on the medical history eCRF. If the onset of an event occurred before the subject entered the trial (e.g., any pre-planned hospitalisation for conditions like cosmetic treatments or for non-emergency routine visits for a pre-existing condition), the hospitalisation would not lead to an AE being classified as serious unless, in the view of the investigator, hospitalisation was necessary due to a worsening of the pre-existing condition.

Results in persistent or significant disability/incapacity.

 Note: The term "disability" means a substantial disruption of a person's ability to conduct normal life functions, in the opinion of the investigator.

Is a congenital anomaly/birth defect.

Is an important and significant medical event (medically significant) that may not be immediately life threatening or resulting in death or hospitalisation but, based upon appropriate medical judgment, may jeopardize the subject or may require intervention to prevent one of the other outcomes listed above.

Any suspected transmission via a medicinal product of an infectious agent is also considered a serious adverse event.

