9.2.2 Inclusion Criteria

The eligibility criteria for patients enrolled in the PER are:

- Adult (≥18) pregnant females exposed to lomitapide at any time within 30 days prior to first day of the LMP or during pregnancy.
- Patients who have the ability to understand the requirements of the study.
- Patients who have provided written consent for participation.

A patient may first provide oral consent on a recorded line if she is enroling herself. The CC will then send the patient a consent form for signature, to be returned in a provided postage-paid envelope. Following completion of oral consent, collection of enrolment data will proceed. If a physician obtains informed consent, the physician will indicate to the CC that verbal consent was obtained. The physician will then be sent a consent form for completion by the patient at her next visit.

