9.2.4 Prospective and Retrospective Pregnancy Definitions

In order to reduce the bias that may occur when outcome information is known prior to enrolment, eligible women are advised to enrol in the PER as soon as their pregnancy is known, preferably in the first trimester before the condition of the foetus has been assessed through prenatal testing. In order to determine the impact of such a bias, pregnancy reports and outcomes will be classified as either prospective or retrospective and will be analysed separately.

Confidential Page 21 of 54

The criteria for prospective pregnancies are:

Prospective pregnancies will include patients who are enrolled after exposure to lomitapide but before the outcome of the pregnancy is known. An exception will be made that women who have undergone prenatal testing that could provide knowledge of the outcome of pregnancy will be considered as a prospective report if the outcome of the testing is normal.

Note: Because early prenatal testing is so prevalent, it may be difficult to achieve adequate numbers of prospectively identified patients if all pregnancies with prior prenatal testing are excluded from the prospective analysis. Therefore, the primary analysis includes pregnant women enroled prior to outcome but after a prenatal test as long as the test does not indicate an abnormality. However, this practice could potentially bias the results by lowering the overall risks of birth defects. To examine this possible source of bias, the analysis will also be conducted excluding the subgroup of women who reported negative prenatal testing at the time of enrolment.

All other patients will be counted as retrospective pregnancies.

The retrospective and prospective pregnancies will be collected in a similar fashion, but treated separately as part of any analyses or reports.

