9.3.4.2 PER Contact Schedule

In countries that allow contact with the patient and the HCP, during the course of the pregnancy the CC will contact the patient once per trimester. In countries with contact restricted to HCPs, during the course of the pregnancy the CC will contact the patient's HCP once per trimester.

Regardless of country of origin of the report, the patient's HCPs will be contacted at 6 to 7 months of gestation for the Prenatal Follow-Up and within 4 weeks after the EDD for Pregnancy Outcome Follow-Up. The infant's HCP will be contacted by the enroling HCP or by the CC when the infant is 12 weeks of age and at 12 months of age for paediatric follow-up.

The data collection schedule is outlined in Table 1 and Table 2.

Confidential Page 26 of 54

Table 1: Data Collection Schedule in Countries with Data Collection Restricted to HCPs

DATA COLLECTION	REGISTRATION BY LOMITAPIDE PRESCRIBER WITH CC	CC CONTACT WITH THE HCP AT EACH TRIMESTER	6 TO 7 MONTHS OF GESTATION FOR THE PRENATAL FOLLOW- UP	CC CONTACT WITH PRACTITIONER(S) AT THE PREGNANCY OUTCOME FOLLOW- UP WITHIN 4 WEEKS AFTER THE EDD	HCP OR CC CONTACT WITH THE INFANT'S HCP AT THE PAEDIATRIC FOLLOW-UP AT 12 WEEKS OLD AND 12 MONTHS OLD ¹
Consent	X				
Patient Demographics and Pregnancy History	X				
Lomitapide Use	X	X	X	X	X (if mother is nursing)
Concomitant Medications	X	X	X	X	X
Medical History	X				
Pregnancy Outcome				X	
Paediatric History and Examinations				X	X
Serious Adverse Events (Pregnancy-Related)		X	X	X	X

¹ The 12-week follow up should be conducted +/- one week.

Confidential Page 27 of 54

Table 2: Data Collection Schedule in Countries with Data Collection from Patients or HCPs

DATA COLLECTION	REGISTRATION/ ENROLMENT	CC CONTACT WITH THE PATIENT AT EACH TRIMESTER	CC CONTACT WITH THE PATIENT'S HCP(S) AT THE PRENATAL FOLLOW- UP, 6 TO 7 MONTHS OF GESTATION	CC CONTACT WITH THE HCP(S) AT THE PREGNANCY OUTCOME FOLLOW- UP ¹ WITHIN 4 WEEKS AFTER THE EDD	CC CONTACT WITH THE INFANT'S HCP AT THE PAEDIATRIC FOLLOW-UP AT 12 WEEKS AND 12 MONTHS OLD ^{2,3}
Consent ⁴	X				
Patient Demographics and Pregnancy History	X				
Contact Information	X	X	X		
Lomitapide Use	X	X	X	X	X (if mother is nursing)
Concomitant Medications	X	X	X	X	X
Medical History	X				
Pregnancy Status/ Outcome		X	X	X	
Paediatric History and Examinations				X	X
Serious Adverse Events (Pregnancy Related)		X	X	X	X

Confidential Page 28 of 54

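### Section 11.3 judges hospitalisation-based seriousness from registry entry, although every woman enters after exposure, so some hospitalised events in exposed time default to non-serious medical history

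*Protocol*

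**What the plan says.** Under the hospitalisation criterion, Section 11.3 gives a recording rule: "A pre-existing event or condition that results in hospitalization should be recorded on the medical history eCRF". It then gives a seriousness rule: "If the onset of an event occurred before the subject entered the trial", "the hospitalisation would not lead to an AE being classified as serious". There is one exception, where in the investigator's view "hospitalisation was necessary due to a worsening of the pre-existing condition". The examples in brackets are admissions arranged in advance and routine, non-urgent visits.

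On the order of exposure and entry, Section 9.2.2 admits "pregnant females exposed to lomitapide at any time within 30 days prior to first day of the LMP or during pregnancy". Section 9.2.4 adds: "Prospective pregnancies will include patients who are enrolled after exposure to lomitapide but before the outcome of the pregnancy is known". All other patients are retrospective. Section 9.5 counts as retrospective, among others, pregnancies from previous studies and spontaneous or literature reports whose outcome is already known.

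On collection, Tables 1 and 2 in Section 9.3.4.2 mark Medical History at registration only. The Table 1 row that begins "Serious Adverse Events (Pregnancy-Related", like its counterpart in Table 2, is blank at registration and marked from the trimester contacts onward.

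**The concern.** Treating an event that began before entry as pre-existing makes sense when entry precedes the first dose, because everything before entry is then unexposed. In this registry the order is reversed. Entry never marks the start of exposure, and no drug is supplied by the study. The interval from first exposure to enrolment is on-drug or post-exposure time, often within the index pregnancy, yet the rule treats it as baseline.

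What is at stake is the serious adverse event record. A hospitalised event from that interval can be denied serious status because of when the woman happened to enrol. Under Section 11.4 a SUSAR must be serious, so an unexpected event suspected to be related to the drug, and serious through hospitalisation alone, could not qualify either.

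**Working it through.** The plan gives no figure on this point, so the check sets the provisions side by side and follows cases through them.

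**Anchors used by each provision**
- Section 11.2, adverse event definition: anchored to use of the product.
- Section 11.6, relatedness: one factor is the timing of onset relative to the start of lomitapide.
- Section 11.3, hospitalisation: anchored to study entry.
- Section 11.3, all other seriousness criteria: no entry cut-off.

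Only the hospitalisation rule looks to entry. Since Section 9.2.2 makes exposure a condition of entry, an interval between first exposure and entry exists for every participant.

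**Cases**
1. *Acute event after exposure, admitted before enrolment.* Onset precedes entry. If the event needed admission from its onset, no existing condition worsened, so the exception does not reach it. Result: not serious by hospitalisation, and recorded as medical history.
2. *Event that began after exposure, managed as an outpatient at enrolment, with unplanned admission later.* The worsening exception would ordinarily apply. Result: usually still serious, subject to the investigator's judgement.
3. *Woman enrolled after the pregnancy outcome.* Her events up to that outcome all precede entry. Result: the default in case 1 applies across the whole pregnancy.
4. *Event that is fatal, life-threatening, disabling, a congenital anomaly or medically significant.* Result: serious whenever it began.
5. *Event with onset after enrolment.* Result: unaffected.

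The gap therefore consists of cases 1 and 3, plus whatever part of case 2 is not judged a worsening, and within these only events whose sole ground for seriousness is hospitalisation.

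**Interaction with the schedule.** The blank SAE row at registration reinforces the gap, because the first contact has no place for a serious event that has already occurred. Marking that row would not be enough by itself, since the definition would still make the hospitalisation non-serious.

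**Size.** An estimate would need the timing of enrolment, the rate of hospitalised events before and after it, and the fraction of those that meet no other criterion. The document gives none of these.

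**The case against.** The strongest reply has four parts.

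- *The rule is meant for elective care.* Its only examples are planned or routine admissions, and reading it to cover an acute event on drug sits badly with Section 11.2. The intent is plausible, but the examples are introduced as examples and the operative condition is onset before entry. If only elective admissions are meant, the text should say so.
- *The worsening exception and the other criteria catch most events.* This largely stands. The exception covers most admissions after enrolment, and the criterion that begins "Is an important and significant medical event (medically significant" would very likely catch something like a cardiac event. Neither reliably covers an acute admission before enrolment. Both replace a plain fact, the admission, with a judgement made case by case.
- *Nothing is lost.* This stands. Section 9.4 collects pregnancy complications, including adverse drug reactions, with dates. The events remain in the database without serious status.
- *No planned analysis is biased.* This stands for the primary outcome, since a congenital anomaly has its own criterion. Sections 9.7 and 9.7.2 define no serious adverse event frequency and no comparison of such frequencies between women. A reader might infer that a planned SAE rate is biased low, but the protocol states no such rate. The fault is in a safety definition, which Section 11.3 itself fixes and does not leave to the SAP.

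**Conclusion.** The point holds in a limited form. The cut-off in Section 11.3 does not fit a registry entered after exposure and conflicts with Sections 11.2 and 11.6. By default it denies serious status to hospitalised events that began after exposure but before enrolment, unless worsening is judged or another criterion is met. Acute admissions before enrolment and retrospective reports carry most of the effect. The conclusion assumes that entering the trial means enrolment in the registry, the only natural reading here.

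Two stronger readings are not supported. A reader might infer that all serious events of the first trimester disappear for a woman who enrols at its end. They do not: only those serious through hospitalisation alone, without worsening, are reclassified, and their data are kept.

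A reader might also size the problem by the share of time before enrolment. Assume enrolment at 12 weeks, so 30 + 7 × 12 = 114 days lie before entry. Over 30 + 280 = 310 days, from 30 days before the LMP to 40 weeks, the share is 114/310 = 36.8%. If the 12 months of infant follow-up are added, it is 114/(310 + 365) = 114/675 = 16.9%. The answer moves with the chosen denominator and an assumed enrolment week, and it counts days, not events. No share of serious adverse events follows from it.

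The change is worth making because it is cheap and concerns a safety definition. It does not threaten the registry's main result.

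**What to change.** - In Section 11.3, replace the entry-based cut-off with an exposure-based one consistent with Section 11.2 and with eligibility: onset before the start of the eligible exposure window (30 days before the first day of the LMP) or, if later, before first lomitapide use.
- Limit the medical-history route to conditions with onset before that point and to pre-planned or routine admissions.
- Mark the serious adverse event row at registration in Tables 1 and 2.
- Add an eCRF flag for onset before enrolment, and tabulate flagged events separately from those arising after enrolment.

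Use the LMP-based window of Section 9.2.2, because Sections 4.2 and 7 also describe the 30 days as counted from conception. Under this cut-off an event that began on lomitapide before the window would still be pre-existing. That follows the registry's own eligibility window, and the text should state it openly.

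The cost is a short rewrite in Section 11.3, one mark in each table, one eCRF field, and seriousness and causality assessment by the reporting HCP for the added events. Events before enrolment will be partly recalled; the separate tabulation keeps that visible.
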